## **Outcome Measures**

- Primary
  - **Incidence of post-operative pulmonary complication within 14 days after surgery**
    - Postoperative pulmonary complication will be defined as
      - Atelectasis or infiltrate diagnosed by radiologist on any postoperative chest radiograph within first 14 days or discharge (whichever occurs first)
      - Pneumonia
        - *Diagnosis is suggested by a history of cough, dyspnea, pleuritic pain, or acute functional or cognitive decline, with abnormal vital signs (e.g., fever, tachycardia) and lung examination findings. Diagnosis should be confirmed by chest radiography or ultrasonography.* [15]
    - Chronic pulmonary obstructive disease exacerbation
      - *An event in the natural course of the disease characterized by a change in the patient's baseline dyspnea, cough, and/or sputum and beyond normal day-to-day variations, that is acute in onset and may warrant a change in regular medication in a patient with underlying COPD* [16]
    - Adult respiratory distress syndrome (Berlin definition)
    - Need for reintubation/mechanical ventilation
    - Need for non-invasive mechanical ventilation
  - Secondary
    - **Time to tracheostomy decannulation** (half days)

NCT05362526

IRB202102700

9/22/22

- **Hospital length of stay after surgery** (half days)
- **Need for antibiotics for pulmonary complication** (escalation to broad spectrum, addition of a second antibiotic, antibiotics past post-operative day 7)
- **Need for pulmonary physiotherapy** (acapella, flutter, etc.)
- **Discharge destination:** Home vs nursing facility vs rehabilitation

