## **Background:**

Major head and neck surgery can come with considerable postoperative risk due to prolonged surgical procedures and time under anesthesia, that often directly involve the airway. Postoperative pulmonary complications are quite common after major head and neck surgery, estimated to be around 18.8-47%, and are increased in those requiring tracheostomy [1-5]. Head and neck oncology surgical patients are at high risk due to the high prevalence of preexisting cardiopulmonary disease, further complicated by a higher proportion of smokers [6]. The patients then undergo long surgeries with general anesthesia, often followed by prolonged immobilization during their recovery. The majority of these patients also undergo elective tracheostomy for airway protection. The tracheostomy can further increase risk for pulmonary complications, because it naturally bypasses the airways natural physiologic warming and humidification system. This causes pathological changes in the lower airways, including damage to the ciliated tracheal mucosa, thickening of airway secretions, and loss or reduction of mucociliary transport [7]. All of

NCT05362526  
IRB202102700  
9/22/22

these pathological changes can lead to pneumonia. While not often fatal in this population, pneumonia can still result in prolonged length of stay, need for intensive critical care, increased use of broad-spectrum antibiotics, and lengthen the time to tracheostomy decannulation [4].

The current standard for oxygen and humidification postoperatively is delivered via cool mist from an aerosol tracheostomy collar. Studies have shown this system is inadequate, as humidification delivered at room air causes mucociliary damage, resulting in increased airway secretion production and retention. Ultimately, this can cause serious complications like mucous plugging and pneumonia [8].

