## **Statistical Analysis**

### Sample Size Rationale

A sample size of 164 patients, 82 in each arm, is sufficient to detect a clinically important difference of 20% in the proportion of postoperative pulmonary complications between arms using a two-tailed z-test of proportions with 90% power and a 5% level of significance. This 20% difference represents 10% of postoperative pulmonary complications using HFOT and 30% of postoperative pulmonary complications in the control arm. Assuming a 10% rate of withdrawal, we will need to recruit 91 patients per arm to be adequately powered to detect the difference.

An interim analysis of the proportion of postoperative pulmonary complications is planned after 100 subjects (50:50) are enrolled to assess whether there will be overwhelming evidence of a benefit from HFOT, as compared with conventional oxygen therapy, or of harm in any study group. As a consequence, the p-value for the primary comparison between the two arms will be adjusted to conserve an overall significance level of 0.05[17]. Descriptive summaries will be frequencies and percentages for categorical variables and means, standard deviations, medians, and quartiles for continuous variables. The primary analysis will compare the difference in the proportion of postoperative pulmonary complications

between the intervention group and the control group. This difference is assessed using univariate analyses and ANCOVA (Analysis of Covariance) models. Demographic and baseline characteristics between groups are assessed using the non-parametric Wilcoxon Rank-Sum test for continuous data, and Pearson Chi-squared test or Fisher's Exact test (when expected frequencies are small) for categorical data. The secondary outcomes will be analyses using the same statistical methods, based upon the data distributions. Data analyses will be performed by a statistician with the Center for Data Solutions.

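### Death is in no outcome and is not named in the interim harm look, so some deaths would count as complication-free, as short stays, or not at all

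*Combined protocol and SAP*

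**What the plan says.** The primary outcome (Outcome Measures) is "Incidence of post-operative pulmonary complication within 14 days after surgery". Its components are atelectasis or infiltrate on a radiograph, pneumonia, COPD exacerbation, ARDS, invasive ventilation ("Need for reintubation/mechanical ventilation") and non-invasive ventilation. The radiographic component stops at day 14 or at discharge if that comes sooner. Death is not a component.

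The secondary outcomes are time to decannulation, "Hospital length of stay after surgery", antibiotics for a pulmonary complication, pulmonary physiotherapy and discharge destination. The destination categories are "Home vs nursing facility vs rehabilitation". None of these outcomes has a rule for a patient who dies.

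On the interim look, Sample Size Rationale says: "An interim analysis of the proportion of postoperative pulmonary complications is planned after 100 subjects (50:50) are enrolled". Its purpose is to find overwhelming benefit "or of harm in any study group". Harm is not defined further and mortality is not mentioned.

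Four other places bear on the point:
- Oxygen Protocols schedules a chest film for every patient at the start of postoperative day 4.
- The section on events that could lead to withdrawal lists patients whose hospital stay is under 4 days, and excludes most patients who return to the operating room.
- Clinic Follow Up Appointments provides adverse-event checks at visits and a contact at day 12.
- Data Safety Monitoring Board has the principal investigator monitor adverse events and report them to the IRB.

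**The concern.** Death ends the period in which a complication can be recorded, and it ends the hospital stay. If it has no place in the outcome definitions, it lowers the complication proportion and shortens length of stay in the arm where it happens. Those are the measures behind Specific Aims 1a and 1c. A patient who dies with the tube in place has no decannulation time (Aim 1b), and the plan does not say whether that patient is dropped, censored or treated as having had a competing event.

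The interim look has the same gap. A review intended to detect harm, but built on the complication proportion alone, would not set deaths in one arm against deaths in the other. The trial is unblinded and has no independent monitoring board, so a comparison fixed in advance is worth more here than it would be elsewhere.

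**Working it through.** **1. How each kind of death is handled as written.**
- *Death after a listed component (for example ARDS or reintubation):* already counted as a complication. No gap in the primary outcome.
- *Death in hospital after a clear day-4 film, with no listed component:* counted as complication-free. A death on day 5 gives a stay of 10 half days, which reads as favourable, and there is no valid discharge destination.
- *Death after discharge but within 14 days, with no listed component:* counted as complication-free.
- *Death before day 4:* may be withdrawn under the 4-day rule, which does not mention death. The patient then leaves the comparison.

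**2. The plan's own figure.** Inputs from Sample Size Rationale: 30% against 10%, two-sided 5% level, 90% power. With the pooled-variance z-test,

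n = [1.960·√(2·0.20·0.80) + 1.2816·√(0.30·0.70 + 0.10·0.90)]² / 0.20² = (1.1087 + 0.7019)² / 0.04 = 82 per arm.

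This reproduces the stated 82.

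**3. Possible distortion of the primary result.** The documents give no death rate, so the excess is assumed. Take a true rate of complication or death of 30% in both arms and 82 analysed per arm. Let a fraction m of HFOT patients die in excess, each death replacing a complication that would have been recorded. The apparent HFOT rate is p = 0.30 − m. With p̄ the mean of 0.30 and p, the chance of a significant result favouring HFOT is

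Φ{[√82·m − 1.960·√(2p̄(1−p̄))] / √(0.21 + p(1−p))}.

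For m = 0.01: (0.0906 − 1.2641)/0.6449 = −1.82, so Φ = 3.4%. The last column repeats the calculation with only 30% of the excess deaths replacing a recorded complication, so that p = 0.30 − 0.3m.

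| Assumed excess HFOT deaths | Patients among 82 | Apparent HFOT rate | Chance of false benefit (nominal 2.5%) | If only 30% replace a complication |
|---|---|---|---|---|
| 1% | 0.8 | 29% | 3.4% | 2.8% |
| 2% | 1.6 | 28% | 4.7% | 3.0% |
| 5% | 4.1 | 25% | 10.7% | 4.0% |

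These use the unadjusted 5% level and ignore the planned interim adjustment.

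**4. How near the boundary it must be.** With 25/82 control events, 14/82 on HFOT gives z = 2.02 and 15/82 gives z = 1.82. One or two deaths therefore change the conclusion only when the result is already close.

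**5. What a table of deaths can show.** By Fisher's exact test, five deaths against none gives p = 0.059 at 82 per arm and p = 0.056 at 50 per arm (the interim). Six against none at 82 per arm gives p = 0.028. The table is for safety review and is not a powered test.

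**6. Cost of putting death into the primary composite.** If deaths without a listed component are 1%, 2% or 3% in both arms, the rates become 31 v 11, 32 v 12 and 33 v 13%. Power at 82 per arm falls from 90% to 88.9%, 87.8% and 86.8%. Restoring 90% needs 86, 89 and 91 per arm.

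**The case against.** The strongest reply is that the gap is narrow and already partly covered. Many respiratory deaths would first meet ARDS, reintubation or pneumonia and so be counted. Every patient still in hospital on day 4 is due a film, and any atelectasis or infiltrate on it counts. Deaths would reach the investigator and the IRB as adverse events. If deaths are equal in the two arms, their effects largely cancel. All of this stands and limits the size of the problem. It does not supply a scoring rule or a comparison between arms.

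A reader might infer more than the documents support, in four ways:
- *That the trial cannot see deaths.* Adverse-event monitoring would pick them up. What is missing is a planned tabulation by arm.
- *That deaths would make HFOT look good.* The Background ties airway damage and retained secretions to the control therapy ("Ultimately, this can cause serious complications like mucous plugging and pneumonia"). Unscored deaths of that kind would lower the control rate and count against HFOT. The documents give no mechanism for excess deaths on HFOT, so the calculation above shows what is possible and does not predict it.
- *That the cited feasibility trial of 20 patients puts a bound on mortality.* The protocol reports neither its deaths nor its arm sizes, so no bound can be computed.
- *That death must join the primary composite.* That is a trade-off. It changes a pulmonary endpoint and costs some power.

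**Conclusion.** The point holds as a gap in outcome definition and safety comparison. Death is in no outcome, in no discharge category and not named in the interim harm look, and the document does not say how a death is scored. The deaths affected are those with no prior listed component, those after discharge, and early ones that may be withdrawn.

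The effect on the primary result is small at low mortality: about 3.4-4.7% against a nominal 2.5% for a 1-2% excess in the HFOT arm. It becomes material at about 5% (10.7%). These figures assume that all excess deaths fall on HFOT and that each replaces a recorded complication. With 30% replacement, the range over the same 1-5% excess is 2.8-4.0%. The death rates are assumptions. The omissions for length of stay, decannulation and discharge destination do not depend on any assumed rate, although how much they matter does.

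**What to change.** 1. Report all-cause death within 14 days by arm as randomised, including deaths among withdrawn patients, as a safety outcome. Tabulate it at the interim look beside the primary proportion.
2. For length of stay, rank in-hospital death as the worst outcome and compare arms with the rank-sum test. The plan already names that test and says secondary outcomes will use the same methods. For time to decannulation, treat death as a competing event.
3. Add a category for death in hospital to discharge destination.
4. Keep the pulmonary composite as the primary outcome, and add a sensitivity analysis of pulmonary complication or death within 14 days.

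The cost is wording, a little more analysis and a less simple length-of-stay summary. The sample size does not change, because the primary outcome does not. The chart and the planned visits over the first two months should supply vital status. The day-12 contact falls short of day 14, so status at day 14 should be confirmed from those sources.

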### **Data Collection**

- Data will be recorded in the subject's medical record list and in their medication administration record. These entries are time stamped at administration. Research data will be collected in REDcap database.

### **Patient Privacy and Protection**

- Identifiable information will be used to monitor clinical records and identify subjects for the study.
- Each participant enrolled in the study will be assigned a participant ID number. The participant ID number will be used on all forms containing data and information from the study.
- Identifiable information (name, date of birth, or MRN) will only be used for data acquisition of a master list and all other PHI used of the participants' names and participant ID numbers will be kept on an institutional server and on the dedicated UF research drive provided by the research department. The master list will be retained in a password protected institutional server for 3 years and will then be

destroyed per institutional guidelines. The de-identified data will be retained indefinitely in a password protected institutional server.

- Data using the participant ID number will be kept on an institutional server and on the dedicated UF research drive
- All data will be stored in REDCap and will later be used for data analysis.
- Consents will be a hard copy and kept in the designated regulatory binder located in the study coordinator's office in a locked cabinet.
- It is possible that your research information, with all personally identifiable information removed, could be used for future research studies or distributed to another investigator for future research studies without additional informed consent from you or your legally authorized representative.

## **Statistical Analysis**

### Sample Size Rationale

A sample size of 164 patients, 82 in each arm, is sufficient to detect a clinically important difference of 20% in the proportion of postoperative pulmonary complications between arms using a two-tailed z-test of proportions with 90% power and a 5% level of significance. This 20% difference represents 10% of postoperative pulmonary complications using HFOT and 30% of postoperative pulmonary complications in the control arm. Assuming a 10% rate of withdrawal, we will need to recruit 91 patients per arm to be adequately powered to detect the difference.

An interim analysis of the proportion of postoperative pulmonary complications is planned after 100 subjects (50:50) are enrolled to assess whether there will be overwhelming evidence of a benefit from HFOT, as compared with conventional oxygen therapy, or of harm in any study group. As a consequence, the p-value for the primary comparison between the two arms will be adjusted to conserve an overall significance level of 0.05[17]. Descriptive summaries will be frequencies and percentages for categorical variables and means, standard deviations, medians, and quartiles for continuous variables. The primary analysis will compare the difference in the proportion of postoperative pulmonary complications

between the intervention group and the control group. This difference is assessed using univariate analyses and ANCOVA (Analysis of Covariance) models. Demographic and baseline characteristics between groups are assessed using the non-parametric Wilcoxon Rank-Sum test for continuous data, and Pearson Chi-squared test or Fisher's Exact test (when expected frequencies are small) for categorical data. The secondary outcomes will be analyses using the same statistical methods, based upon the data distributions. Data analyses will be performed by a statistician with the Center for Data Solutions.

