High flow oxygen therapy (HFOT) delivers heated and humidified oxygen, which has been shown to have multiple benefits, the first being able to delivery physiologically optimal heated humidification, as well as the ability to deliver positive airway pressure. By mimicking the optimal airway temperature and humidification, patients have less respiratory secretions and have improved clearance, preventing infection [9,10]. Positive airway pressure has been shown to improve oxygenation via increased end-expiratory lung volumes, and is important postoperatively as it can reduce lower airway collapse and atelectasis [11]. Meta-analysis of clinical trials, examining prophylactic use of HFOT during the immediate postoperative course for other major operations (cardiac, intrathoracic, abdominal), and showed a reduction in reintubation and the need to escalate respiratory support, when compared to conventional oxygen therapy [13].

Use of high flow after major head and neck surgery is generally unexplored. To date, only one study evaluates use of prophylactic HFOT tracheostomy collar after major head and neck surgery. In this small controlled trial (n=20), they concluded that HFOT was safe and feasible for this patient population [2].

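### The single interim look sets the same overwhelming-evidence standard for harm as for benefit and gives no separate harm threshold

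*Combined protocol and SAP*

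**What the plan says.** All of the interim plan is in Statistical Analysis, under Sample Size Rationale. One interim analysis of the primary outcome proportion is "planned after 100 subjects (50:50) are enrolled". Its purpose is to see whether there is "overwhelming evidence of a benefit from HFOT, as compared with conventional oxygen therapy, or of harm in any study group". The next sentence says that "the p-value for the primary comparison between the two arms will be adjusted to conserve an overall significance level of 0.05", citing reference 17, the O'Brien-Fleming paper. The design test is two-sided: the sample size was found "using a two-tailed z-test of proportions with 90% power and a 5% level of significance".

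The section gives no boundary value, no separate criterion for harm, and no action to follow from crossing or not crossing.

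Elsewhere, the Data Safety Monitoring Board section describes no independent board. It has the principal investigator monitor adverse events and report them to the IRB. On prior evidence in this population, the Background says: "Use of high flow after major head and neck surgery is generally unexplored". It cites one earlier study, of 20 patients.

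**The concern.** O'Brien-Fleming boundaries are strict early so that a chance result at an interim look does not become a claim of efficacy. That protection has no counterpart on the harm side. A pause or review prompted by excess complications on HFOT cannot produce a false claim that HFOT works. The same strictness applied to harm therefore mainly makes a real excess less likely to be flagged.

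This look is the only between-arm comparison planned before the end of the trial. If its harm criterion is as strict as its benefit criterion, a large true excess of pulmonary complications on HFOT would more often than not meet no stated criterion at that point.

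**Working it through.** **Inputs (Sample Size Rationale unless noted).** Two-sided 5% level and 90% power. Rates: "This 20% difference represents 10% of postoperative pulmonary complications using HFOT and 30% of postoperative pulmonary complications in the control arm". Size: "A sample size of 164 patients, 82 in each arm". Recruitment: "Assuming a 10% rate of withdrawal, we will need to recruit 91 patients per arm", so 182 in all. The look is at 50 per arm. The Background puts the complication rate at 18.8-47%.

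**1. The plan's own figure.** With pooled variance under the null and mean rate 0.20:

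n = [1.960 × √(2 × 0.2 × 0.8) + 1.282 × √(0.1 × 0.9 + 0.3 × 0.7)]² / 0.20² = (1.1087 + 0.7019)² / 0.04 ≈ 81.96, so 82 per arm. This matches.

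**2. The boundary, if O'Brien-Fleming is applied symmetrically with two looks.** The information fraction t is 100/164 = 0.610 or 100/182 = 0.549. In the classic form the interim boundary is C/√t, with C solved so that the overall two-sided level is 0.05. In the Lan-DeMets form, each tail of 0.025 spends 2[1 − Φ(z₀.₀₁₂₅/√t)] by the interim, where z₀.₀₁₂₅ is the upper 1.25% normal point.

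| t | Classic: C, then boundary (two-sided p) | Lan-DeMets boundary (two-sided p) |
|---|---|---|
| 0.610 | 1.994, 2.55 (0.0107) | 2.64 (0.0082) |
| 0.549 | 1.984, 2.68 (0.0074) | 2.81 (0.0050) |

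**3. Counts needed with 15/50 control events.** For HFOT count y and control count x, the pooled rate is p = (x + y)/100 and z = [(y − x)/50] / √[p(1 − p) × 2/50].

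| HFOT | Ratio to 15/50 | z | Crosses |
|---|---|---|---|
| 27/50 (54%) | 1.80 | 0.24 / √(0.42 × 0.58 × 0.04) = 2.43 | none of the four |
| 28/50 (56%) | 1.87 | 0.26 / √(0.43 × 0.57 × 0.04) = 2.63 | only 2.55 |
| 29/50 (58%) | 1.93 | 0.28 / √(0.44 × 0.56 × 0.04) = 2.82 | all four |

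**4. Other control rates.** With 9/50 (18%), HFOT needs 21-22/50, a ratio of 2.33-2.44. With 24/50 (48%), it needs 37-38/50, a ratio of 1.54-1.58. These two rates roughly span the Background range.

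**5. Chance of crossing for harm.** This sums binomial probabilities over all pairs of counts at 50 per arm, with control at 30%.

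| Threshold | True HFOT 50% | True HFOT 45% | True HFOT 30% |
|---|---|---|---|
| z ≥ 2.55 | 30.8% | 15.6% | 0.5% |
| z ≥ 2.64 | 26.8% | 13.5% | 0.4% |
| z ≥ 2.68 | 25.6% | 12.7% | 0.4% |
| z ≥ 2.81 | 23.2% | 10.8% | 0.3% |
| z ≥ 1.96 (one-sided 0.025) | 54.6% | 34.4% | 2.5% |

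**6. What a one-sided 0.025 guideline would need.** Against 15/50, 25/50 gives z = 0.20 / √(0.40 × 0.60 × 0.04) = 2.04 and crosses; 24/50 gives 1.85 and does not. At the planned 10% on HFOT against 30%, the chance of a false harm signal is about 4 in a million.

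**The case against.** The strongest objection is that no harm boundary is written down. The O'Brien-Fleming citation is attached to the adjustment of the p-value for the primary comparison, and the harm standard is given in words only. A reader might infer that the plan fixes an O'Brien-Fleming boundary for harm. It does not; the z-values above show what the only cited method would imply. This stands as a limit on the numbers. It does not supply a harm criterion: on any reading the text sets one verbal standard for both directions and nothing more specific for harm.

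A reader might also infer that the trial would carry on while HFOT nearly doubled complications. The documents do not say so. No consequence is prescribed for any interim result, the trial is open-label, patients are screened for adverse events and pulmonary complications at follow-up (Clinic Follow Up Appointments), and the investigator reports to the IRB. Any of these could lead to action. What remains is that none of them compares the arms against a threshold. Nor is near-doubling a general figure, because the ratio needed depends on the control rate.

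Three further points have weight. A symmetric two-sided rule is a legitimate design. The primary outcome counts any atelectasis or infiltrate read by a radiologist (Outcome Measures), so an excess need not be serious harm. The plan also describes both modalities as established (Possible Discomfort and Risks; Data Safety Monitoring Board), and the Background cites supportive evidence from other surgery. These points limit the urgency. They do not explain why a prompt for review should need the same evidence as an efficacy claim.

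**Conclusion.** The point holds as a gap in the interim plan: harm is held to the same overwhelming-evidence standard as benefit, with no threshold of its own. Under a symmetric O'Brien-Fleming reading, 27/50 against 15/50 would meet no criterion, and a true rise from 30% to 50% would be flagged about one time in four (23-31%).

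The size rests on four assumptions: that the cited method governs harm as well as benefit; a pooled z-test; a control rate near 30%; and all 100 patients having an outcome at the look. The last is generous, because the look is timed on enrolment and some patients may be withdrawn or not yet have 14 days of follow-up. Fewer evaluable patients would raise the difference needed.

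The point does not threaten the validity of the final efficacy comparison, and it does not show that the trial would continue in the face of harm. It supports a worthwhile, low-cost addition.

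**What to change.** In Sample Size Rationale, state that O'Brien-Fleming governs the benefit decision. Add a separate, non-binding statistical harm guideline at the same look: for example, excess pulmonary complications on HFOT at one-sided p <= 0.025 (25/50 against 15/50) prompts a review of whether to continue. State that the guideline spends no efficacy alpha, because the benefit boundary is calculated as if it were absent, and that reaching it is a prompt for review and not a formal finding of harm. An excess on conventional therapy is already covered by the benefit boundary.

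The level is the sponsor's choice. Against 15/50, a one-sided level of 0.05 is reached at 23/50 and 0.10 at 22/50, with false-signal rates of about 5% and 10% when both arms are at 30%.

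The cost is a few lines of text and, at 0.025, about a 2.5% chance of an unneeded review if the arms are equal. Loss of power at the planned rates is negligible. The guideline remains imperfect: it would still miss a true rise from 30% to 50% about 45% of the time.

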#### Randomization

- Randomization will be assigned by the study coordinator once the patient completes the consent process.
- Patients will be divided into three subgroups after enrollment: no free flap, free flap, and laryngo-pharyngectomy
- Randomization into COT vs HFOT will be performed based on a block randomization scheme, stratified by subgroup- no free flap, free flap, or laryngo-pharyngectomy.
- This system will be used to ensure well-balanced distribution into these three subgroups and in the two arms.
- The goal will be to always keep enrollment balanced accordingly to the usual volume of no free flap, free flap, or laryngo-pharyngectomy among the two treatment groups.
- The block randomization scheme will be generated by the analyst with the Center for Data Solutions at the UF College of Medicine Jacksonville, FL and it will be uploaded into REDCap before the data collection.

NCT05362526

IRB202102700

9/22/22

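### Randomisation is stratified by three surgical groups, but the primary analysis does not name them or say which test decides

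*Combined protocol and SAP*

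**What the plan says.** The primary outcome is binary: "Incidence of post-operative pulmonary complication within 14 days after surgery" (Outcome Measures).

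Under Randomization, allocation to the two arms is "performed based on a block randomization scheme, stratified by subgroup- no free flap, free flap, or laryngo-pharyngectomy".

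Under Statistical Analysis, Sample Size Rationale, the plan makes three statements about testing:

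- The trial is sized "using a two-tailed z-test of proportions with 90% power and a 5% level of significance", for 30% in controls against 10% with HFOT, with 82 per arm.
- After an interim look at 100 enrolled patients, "the p-value for the primary comparison between the two arms will be adjusted to conserve an overall significance level of 0.05".
- For the primary difference in proportions, "This difference is assessed using univariate analyses and ANCOVA (Analysis of Covariance) models".

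That section does not mention the three surgical groups. It lists no ANCOVA covariates and does not rank the z-test, the univariate analyses and ANCOVA. No other section fills these gaps.

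**The concern.** Two things are left open.

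First, the deciding analysis may ignore the factor used to stratify randomisation. Stratified blocks balance the arms within each surgical group, so differences in risk between groups contribute little to chance differences between arms. An unadjusted test still counts that between-group variation in its standard error. The standard error is then too large, and the test rejects less often than its nominal level. It remains valid but gives up some power.

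Second, the interim adjustment presupposes one identified p-value. The plan has at least two candidates, an unadjusted comparison and ANCOVA, and ANCOVA's covariates are open. The choice could be made after results are seen, in a non-blinded trial with an interim look at the outcome.

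**Working it through.** **1. The plan's own figure.** Inputs from Sample Size Rationale: 10% v 30%, two-sided 5%, 90% power. The pooled z-test formula is

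n = [1.960 × √(2 × 0.20 × 0.80) + 1.2816 × √(0.10 × 0.90 + 0.30 × 0.70)]² / 0.20²

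= (1.1087 + 0.7019)² / 0.04 = 81.96, so 82 per arm.

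This matches the plan, and power at 82 per arm is 90.0%. The same formula gives 63.5% for 30% v 15%. The sample size therefore rests on a test that ignores the strata, and it is correct for that test.

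**2. Why the unadjusted test is conservative.** The documents give neither sizes nor risks by surgical group, so both are assumed here: 82 per arm split 33/33/16, and control risks 18.8%, 33% and 47%. The end values come from the Background, where rates are "estimated to be around 18.8-47%, and are increased in those requiring tracheostomy". That is a range of published rates, used only to set a plausible spread. It is not evidence about these three groups.

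- Overall risk: (33 × 0.188 + 33 × 0.33 + 16 × 0.47) / 82 = 24.614 / 82 = 0.300.
- Variance used by the unadjusted test: 0.300 × 0.700 = 0.2101 (unrounded inputs).
- Actual variance within groups: (33 × 0.1527 + 33 × 0.2211 + 16 × 0.2491) / 82 = 0.1990.
- Ratio: 0.1990 / 0.2101 = 0.947, with square root 0.973.
- Approximate type I error: 2 × [1 − Φ(1.960 / 0.973)] = 4.4%.

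**3. Simulation.** 400,000 trials per scenario, with a single look at 5%, exact balance within groups, and a common odds ratio giving 10% or 15% overall with HFOT. The 15% rate is an assumption; the plan uses only 10%. CMH is the Cochran-Mantel-Haenszel test without continuity correction.

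| Assumed control risks | Type I error, z v CMH | CMH minus z, power at 30% v 10% | CMH minus z, power at 30% v 15% |
|---|---|---|---|
| 30/30/30% | 5.0% v 5.0% | −0.2 points (91.0% v 90.8%) | −0.3 points (64.5% v 64.2%) |
| 20/35/40% | 4.6% v 5.0% | +0.2 points | +0.7 points |
| 18.8/33/47% | 4.4% v 5.0% | +0.5 points (91.5% v 92.0%) | +1.3 points (64.6% v 65.9%) |
| 15/35/50% | 4.1% v 5.0% | +0.8 points | +2.3 points |

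A linear model on arm and surgical group is within about 0.2 points of CMH throughout.

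**4. Sensitivity to the assumptions**

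- *Group sizes.* Splits of 27/28/27, 20/50/12 and 12/45/25, with end risks of 18.8% and 47% and 30% overall, give an unadjusted type I error of 4.2–4.6%. CMH gains 0.3–0.7 points at 30% v 10% and 0.8–1.9 points at 30% v 15%.
- *Withdrawal.* The plan states: "Assuming a 10% rate of withdrawal, we will need to recruit 91 patients per arm". Recruiting 37/36/18 per arm and removing 10% at random, the 18.8/33/47% case gives type I error 4.4% v 4.9%, and power 91.5% v 92.0% and 64.6% v 65.8%.
- *Two looks.* The plan states no information fraction, so two are assumed. At 100/164, the O'Brien-Fleming levels are 0.0107 and 0.0462. The same case gives type I error 4.5% v 4.9%, and power 91.1% v 91.6% and 63.6% v 65.2%. At 90/164, the levels are 0.0074 and 0.0472, giving 4.4% v 5.0%, 91.0% v 91.7% and 63.6% v 65.5%.

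**5. Choosing between results.** Reporting whichever of z or CMH is significant gives at most 5.1% type I error with exact balance and 5.2% with withdrawal, across the scenarios run. Choosing among other ANCOVA covariates cannot be sized from the documents.

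**The case against.** The strongest reply is that little is at stake. The unadjusted test is valid, the stated power holds, and the gain at the planned effect is about half a point in the main scenario. Every figure showing a gain rests on assumed group sizes and risks, and the documents do not say that risk differs between the groups. All of that stands. It is why the point is minor and why the equal-risk case, where stratifying loses slightly, is shown.

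A second reply is that the ambiguity is narrower than it looks. The pooled z-test is equivalent to the uncorrected Pearson chi-squared test, so the z-test and the univariate analysis are probably one and the same. ANCOVA would then be the supporting model, with the strata as its natural covariates. This is a reasonable reading, but the plan does not state it. On that reading the deciding test is also the one that ignores the strata. If ANCOVA with the strata was meant to decide, saying so is the whole correction.

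A third reply is that ANCOVA is usually a method for continuous outcomes, so its use here needs explaining. That is fair. The simulations show that a linear model with group terms performs like CMH in these scenarios, but CMH is the more direct choice for a yes/no outcome.

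**Conclusion.** The concern holds, as a minor point. The plan stratifies randomisation by surgical group, does not commit to using those groups in the primary analysis, and does not identify the analysis that carries the adjusted significance level. The sample size needs no change.

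Under the unequal risks in the table, an unadjusted analysis has type I error of 4.1–4.6%. It gives up 0.2–0.8 points of power at 30% v 10% and 0.7–2.3 points at 30% v 15%. If risks are equal, adjustment costs 0.2–0.3 points. Confidence is high on what the text omits. The sizes are illustrative, because the group sizes and risks are assumed.

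The inflation from choosing between the unadjusted and stratified tests is negligible in the scenarios run. The open covariate list is the part whose effect cannot be estimated.

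**What to change.** In the Statistical Analysis section, name one deciding primary analysis adjusted for the randomisation strata. Suggested wording: *The primary analysis is a Cochran-Mantel-Haenszel test stratified by the three surgical groups used at randomisation, reported with a stratum-weighted risk difference and 95% confidence interval. The interim-adjusted significance level applies to this test at both looks. The unadjusted z-test is a sensitivity analysis.*

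Keeping ANCOVA would also do, provided it is named as the deciding analysis, its covariates are stated to be the three strata, and its use for a binary outcome is explained.

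The cost is a few sentences. The surgical group is known for every patient at randomisation, so no extra data or patients are needed. The only statistical cost is the 0.2–0.3 points of power lost if risk is the same in all three groups.
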